8.7.8.2 Hypoglycemia Events

Hypoglycemia events will be summarized similarly to the treatment-emergent AEs for on-treatment observation periods based on the safety set. In addition, hypoglycemia events will be counted with multiple episodes per participant, if available, and the event rate per person-years will be reported overall and by level.

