If multiple valid values of a variable (efficacy or safety) exist within a same day (and the recorded times of measurement do not identify which of them is the last assessment), the value measured during the scheduled visit will be used as Baseline in the analysis. If none of those values were assessed during a scheduled visit, then all these measurements will be used for the analysis and the average will be calculated to derive the baseline value.

In general, descriptive statistics of quantitative efficacy and safety parameters (result and change from baseline) by scheduled visits will be provided on observed cases (OC; ie, inclusion of only participants having non-missing assessments at a specific visit).

Baseline safety and baseline efficacy results are presented in the safety and efficacy analyses, respectively.

All safety analyses will be performed on the safety analysis set.

Statistical analysis will be performed using SAS Enterprise software Version 9.4 or higher.

Observation period

The observation period will be divided into 3 segments:

- The **pre-treatment period** is defined as the period up to first IMP administration. There are two periods within pre-treatment period. A 2-week screening period and a 2-week run-in period.
- The **on-treatment period** (ie, treatment-emergent (TE) period) is defined as the period from the first IMP administration to the last IMP administration during Visit 7 (Week 16).
- The **post-treatment period** is defined as the period from the end of the on-treatment period to the end of the 2-week safety period. (Week 18)

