4.7.2 Adverse events

All AEs will be collected from the signing of the ICF until the follow-up visit.

General common rules for adverse events

All adverse events (AEs) will be coded to a lower-level term (LLT), preferred term (PT), high-level term (HLT), high-level group term (HLGT), and associated primary system organ class (SOC) using the Medical Dictionary for Regulatory Activities (MedDRA) version currently in effect at Sanofi at the time of database lock.

The AEs (which are recorded on the AE eCRF page, including hypoglycemia events qualifying as AEs) will be categorized as:

- Pre-treatment AEs: AEs that developed, worsened or became serious during the pre-treatment period, defined as the time from the signed informed consent date up to the first administration of the IMP.
- Treatment-emergent adverse events (TEAE)s: AEs that developed, worsened or became serious during the treatment-emergent period defined as the time from the first administration of the IMP (on Day 1) to the last administration of the IMP + 3 days.
- Post-treatment AEs: AEs that developed, worsened or became serious during the post-treatment period defined as the time starting 1 day after the end of the TEAE period up to the end of the study follow-up (2 weeks after the end of treatment period)

Similarly, the deaths will be analyzed in the pre-treatment, treatment-emergent and post-treatment periods.

Pre-treatment safety data will be analyzed using the Screening Analysis Set. Treatment-emergent and post-treatment safety data will be analyzed using the Safety Analysis Set.

The primary focus of AE reporting will be on TEAEs, and AESIs. Pre-treatment and post-treatment AEs will be described separately.

An AE with incomplete or missing date/time of onset (occurrence, worsening or becoming serious) will be classified as a TEAE unless there is definitive information to determine it is a pre-treatment or a post-treatment AE.

If the assessment of the relationship to IMP is missing for an AE, the AE will be assumed to be related to IMP within summary tables. If the severity is missing for one of the treatment-emergent occurrences of an AE, the severity will be imputed with the maximal severity of the other occurrences within the PT. If the severity is missing for all the occurrences, the severity will be left as missing.

Multiple occurrences of the same event in the same participant will be counted only once in the tables within a treatment phase.

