
- Symptomatic Hypoglycemia: defined as any symptomatic hypoglycemia recorded on Hypoglycemic Event Information Library eCRF page responding that symptoms were present with the plasma glucose measurements of < 70 mg/dL (or < 3.9 mmol/L).
- Pseudohypoglycemia: defined as any symptomatic hypoglycemia recorded on Hypoglycemic Event Information Library eCRF page responding that symptoms were present with the plasma glucose measurements of ≥ 70 mg/dL (or ≥ 3.9 mmol/L).

Hypoglycemia events categorized by time of day at which the event occurred by ADA levels, will be provided in a table:

- Nocturnal Hypoglycemia Defined by Time of the Day: Any hypoglycemia event that occurs between 00:00 and 05:59, regardless of whether the participant was awake or woke up because of the event.
- Nocturnal Hypoglycemia Defined by Sleep Status: Any hypoglycemia event that wakes the participant from sleep between bedtime and rising in the morning, i.e., before the morning assessment of fasting prebreakfast SMPG and before any insulin injection. The participant wakes up because of the event.
- Daytime Hypoglycemia Defined by Time of the Day: Any hypoglycemia event that occurs between 06:00 and 23:59.
- Daytime Hypoglycemia Defined by Awake Status: Any hypoglycemia event that occurs between the participant waking up and going to sleep.

Hypoglycemia observation periods

- Pre-treatment hypoglycemia events are events that developed or worsened or became serious from the signed informed consent date up to first administration of the IMP.
- Treatment-emergent hypoglycemia events are those that developed or worsened or became serious during the on-treatment period arising from the time of the first IMP administration (on Day 1) up to 1 day after the last IMP injection.
- Post-treatment hypoglycemia events are events that developed or worsened or became serious during the post-treatment period arising 1 day after the end of the TEAE period up to the end of the study follow-up (2 weeks after the end of treatment period)

Descriptive analysis will summarize hypoglycemia events in a table (repeat for subgroups [i.e., OAD only at baseline, OAD plus GLP-1 RA at baseline, ≥ 65 years of age, < 65 years of age]):

- Overall number and percentage of participants with at least 1 hypoglycemia event (for overall and each observation period) and number of hypoglycemic events (for overall and each observation period)

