- Number and percentage of participants with at least 1 hypoglycemia event and number of hypoglycemic events, by ADA classification levels

- Number and percentage of participants with at least 1 hypoglycemia event and number of hypoglycemic events, by observation periods
- Documented Hypoglycemia
 - Documented symptomatic hypoglycemia
 - Documented serious symptomatic hypoglycemia
 - Documented non-serious symptomatic hypoglycemia
 - Asymptomatic Hypoglycemia
- Symptomatic Hypoglycemia
- Pseudohypoglycemia
- Nocturnal Hypoglycemia Defined by Time of the Day, overall and by ADA levels
- Nocturnal Hypoglycemia Defined by Sleep Status, overall and by ADA levels
- Daytime Hypoglycemia Defined by Time of the Day: overall and by ADA levels
- Daytime Hypoglycemia Defined by Awake Status, overall and by ADA levels

In addition, rate of on-treatment symptomatic hypoglycemic events (Overall, and by time of day per ADA levels) will be summarized in a table whereas

Hypoglycemic events rate per participant year = Number with hypoglycemic events/Total Person Years

If there are multiple events from an individual participant, all events will be counted.

where Total PY is calculated as below:

Observation period	Total Person Years	Time to event (days)	Censoring time (days)
On-treatment	(cumulative total time to event date for participants with event + cumulative total of censoring time for participants without event)	date of event -first dose date +1	(last dose date+1) -first dose date +1

Participants with symptomatic hypoglycemia events, and participants with severe hypoglycemia events will be displayed in listings. A figure will be provided showing the time to the first severe or documented ADA Level 3 symptomatic hypoglycemia during on-treatment period.

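### Hypoglycemia on days +2 and +3 after the last dose falls in no by-period row, and SAP 4.7.3 specifies event rates only for symptomatic events although the protocol promises rates overall and by level

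*SAP*

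**What the plan says.** **Observation periods.** SAP 4.7.3 defines treatment-emergent hypoglycemia as events "arising from the time of the first IMP administration (on Day 1) up to 1 day after the last IMP injection". Its next bullet defines post-treatment hypoglycemia as events "arising 1 day after the end of the TEAE period up to the end of the study follow-up". The TEAE period is set in SAP 4.7.2, where it is "defined as the time from the first administration of the IMP (on Day 1) to the last administration of the IMP + 3 days". SAP 4.1 has a further, general on-treatment period, running from "the first IMP administration to the last IMP administration during Visit 7", followed by a post-treatment period with no lag. SAP 4.7.3 asks for participants and events overall and for each observation period.

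**Event rates.** Protocol 8.7.8.2 counts repeat episodes and says that the rate per person-years "will be reported overall and by level". It sets no symptom condition. SAP 4.7 says in general terms that hypoglycemia will be described by the percentage of participants affected and by events per participant year, and leaves the explanation to 4.7.3. There, the only rate with a table and a formula is the "rate of on-treatment symptomatic hypoglycemic events", given overall and by time of day per ADA level. The SAP defines symptomatic hypoglycemia as symptoms together with a glucose value below 70 mg/dL.

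**Declared changes.** SAP Appendix 2 states that nothing departs from the protocol's planned analyses. Table 9 in Appendix 5 lists three changes: the correlation with patient-reported outcomes, the 60-unit association, and CGM compliance. Hypoglycemia rates are not among them.

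**The concern.** The post-treatment hypoglycemia bullet borrows its starting point from the adverse event section, where the window is two days longer. The two hypoglycemia windows therefore do not meet. By-period rows need not add up to the overall row, and the programmer has no rule for an event in between. There is also a clash between tables. SAP 4.7.2 includes hypoglycemia that qualifies as an adverse event, so such an event on day +2 or +3 is treatment-emergent in the AE tables and unassigned in the hypoglycemia tables.

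On rates, overall and confirmed hypoglycemia by ADA level are listed safety endpoints in both documents. The SAP's own description of Level 1 says that values below 70 mg/dL matter whether or not symptoms are severe. A rate confined to symptomatic events leaves out the asymptomatic part of Levels 1 and 2. It also leaves out recorded events without a qualifying glucose value, which the SAP counts under any hypoglycemia. Readers of the report would see a narrower rate than the protocol promised, with no notice of the change.

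**Working it through.** The plan states no figure to reproduce here, so the check is to classify days and to compare texts.

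**1. Classifying days after the last dose.** Inputs: hypoglycemia treatment-emergent end = +1 (SAP 4.7.3); TEAE end = +3 (SAP 4.7.2); post-treatment start = TEAE end + 1 = 3 + 1 = +4 (SAP 4.7.3); follow-up end = +14 (two weeks).

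| Rule | Treatment-emergent | Unassigned | Post-treatment |
|---|---|---|---|
| SAP as written | to +1 | +2, +3 | +4 to +14 (11 days) |
| Post-treatment starts after the hypoglycemia window | to +1 | none | +2 to +14 (13 days) |
| Hypoglycemia window lengthened to +3 | to +3 | none | +4 to +14 (11 days) |

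Exactly two days per participant are unassigned. Either change closes the gap. The first leaves the on-treatment rate window as it is.

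**2. Size of the gap.** For 100 treated participants it is 100 × 2 / 365.25 = 0.55 participant-years. The SAP's censoring time is (last dose date + 1) − first dose date + 1. With the last dose 112 days after the first, this is 114 days, and 100 × 114 / 365.25 = 31.21 participant-years. The ratio is 2 / 114 = 1.75%. This assumes that everyone completes treatment and that person-time is not cut short at an event. It is only a scale: person-time in 4.7.3 stops at last dose + 1, so days +2 and +3 are outside both numerator and denominator of the on-treatment rate.

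**3. Which events get a rate.**

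| Event type | Protocol 8.7.8.2 | SAP 4.7.3 counts | SAP 4.7.3 rate formula |
|---|---|---|---|
| Any hypoglycemia | rate | yes | none specified |
| Each ADA level, regardless of symptoms | rate | yes | none specified |
| Symptomatic, below 70 mg/dL | included above | yes | yes, overall |
| Symptomatic, by ADA level | included above | not listed as such | only within time of day |
| Asymptomatic, below 70 mg/dL | included above | yes | none specified |

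**4. Whether the existing formula can simply be extended.** SAP 4.7.3 counts every repeat event, but for a participant with an event it counts person-time only to the event date. Let participant *i* have *K* events, the first on day *t*, within a full on-treatment time *T*. Reading the event date as that of the first event, the formula puts *K* events over *t* days, whereas counting all events requires *K* over *T*. Since *t* ≤ *T*, the summed denominator is never larger than the full person-time, so the rate is never smaller than the rate on full person-time. It is larger whenever any *t* < *T*. The documents do not give event timing, so the size of the inflation cannot be computed.

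**The case against.** The best defense is that little is lost. Gap events stay in the overall counts, the table by ADA level is not restricted to a period, and symptomatic and severe events are listed individually. The general post-treatment period in SAP 4.1 has no lag and would cover days +2 and +3. Scheduled fasting SMPG ends at Visit 7, so few measured values are likely in those two days. On rates, SAP 4.7 does state an intent to report events per participant year. The symptomatic table in 4.7.3 is introduced as an addition, and it does give ADA levels within time of day. Asymptomatic events are counted and cumulative exposure is reported, so a crude rate could be worked out by hand.

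Most of this stands, and it rules out several stronger readings that a reader might infer:

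- **That gap events vanish from the report.** They are missing only from the by-period rows.
- **That the SAP abandons every rate except the symptomatic one.** Section 4.7 says otherwise in general terms; what is missing is a specification.
- **That the 0.55 participant-years distort a rate.** They enter no planned rate.
- **That different ends for AEs (+3) and hypoglycemia (+1) are themselves an error.** Separate windows are a legitimate choice; the error is the cross-reference between them.
- **That hypoglycemia is the main safety endpoint.** Neither document ranks the safety endpoints.

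The defense does not remove the point itself. The hypoglycemia-specific definitions are the ones that 4.7.3 tells a programmer to apply, and they conflict with 4.1. A general intent that refers to a section with no matching table or formula does not meet the protocol's commitment.

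**Conclusion.** The concern holds in a limited form. Read literally, SAP 4.7.3 leaves two days per participant in no hypoglycemia period. This is a minor cross-reference slip that affects the by-period rows and their agreement with the AE tables. The rate issue matters more: the protocol promises rates overall and by level, whereas the SAP specifies them only for symptomatic events and declares no change. Its effect on the reported rates cannot be given a number, because the documents do not say how many events are expected to be asymptomatic.

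Both parts concern descriptive safety reporting. The primary analysis, the key secondary tests and the on-treatment symptomatic rate as defined do not depend on either. The conclusion rests on taking the specific text of 4.7.3 as governing over the general periods in 4.1, and on reading the TEAE period as that of 4.7.2.

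**What to change.** - In SAP 4.7.3, start the post-treatment hypoglycemia period on the day after the hypoglycemia treatment-emergent window ends, that is, at last dose + 2 days. The AE window can stay at + 3 days.
- Add on-treatment event rates for any hypoglycemia and for each ADA level regardless of symptoms, as protocol 8.7.8.2 requires. Keep the symptomatic rate as an addition.
- For every rate that counts repeat events, use each participant's full on-treatment person-time, from first dose to last dose + 1 day, as the denominator. State that the numerator is the number of events.
- If the sponsor prefers to report only the symptomatic rate, list this in Table 9 with a reason and align Appendix 2.

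The cost is SAP wording and a few table shells. No new data are needed.

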4.7 SAFETY ANALYSES

All safety analyses will be performed on the safety set as defined in [Section 3](#), unless otherwise specified, using the following common rules:

- The analysis of the safety variables will be analyzed descriptively, and no testing is planned. Planned analysis is described in further detail below.

The safety endpoints include number of participants with adverse events (AE), serious adverse events (SAEs), adverse events of special interest (AESIs), overall hypoglycemia, and confirmed hypoglycemia.

Hypoglycemia rates during 16 weeks of treatment, including the percentage of participants with at least 1 hypoglycemia event and number of events per participant year, will be analyzed descriptively in a table. Further explanation is described below in hypoglycemia section.

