4.7.1 Extent of exposure

The extent of study treatment (specifically, insulin glargine) exposure and adherence will be assessed based on the safety set, presented by the following parameters:

- Duration of treatment;
- Mean planned dose, i.e., doses documented in CRF Exposure page;
- Mean actual dose, i.e., doses recorded in diary by participants;
- Minimum planned dose;
- Maximum planned dose;
- Last planned dose, i.e., the planned dose documented in CRF at the last visit;
- Number of participants whose planned dose reached at least 60 units/mL.

The lixisenatide dose will not be presented; instead, a footnote that states the ratio of insulin glargine (in unit/mL) to lixisenatide (in µg/mL) equals 3:1 will be included wherever applicable.

Duration of IMP exposure

The duration of IMP exposure will be calculated as date of the last IMP injection – date of the first IMP injection + 1. If the date of the last dose of IMP (in the eCRFs) is missing, the duration of IMP will be left as missing.

Duration of IMP exposure will be summarized quantitatively using descriptive statistics and categorically as below:

- ≤ 8 weeks
- > 8 weeks to ≤ 16 weeks
- >16 weeks

Additionally, the cumulative duration of treatment exposure will be provided, defined as the sum of days of the duration of treatment exposure for all participants divided by 365.25, and will be expressed in participant years.

A summary of the number and percentage of subjects with any visit impacted by the COVID-19 pandemic may be produced, if applicable. The summary will include the number of visits and assessments impacted, as well as the reasons for the impacted visits/assessments.

Treatment adherence

A given administration will be considered nonadherent if the participant did not take the planned dose of treatment as required by the protocol. No imputation will be made for participants with missing or incomplete data.

The adherence rate for a participant will be defined as the total number of days with a Soliqua 100/33 injection divided by planned number of days with Soliqua 100/33 injection multiplied by 100.

Treatment adherence will be summarized using the mean, SD, median, minimum, maximum and range, using the safety set. In addition, the percentage of participants who have <60%, ≥60% to <80%, ≥80% to ≤100%, and >100% adherence will be summarized.

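### The hypoglycemia rate in SAP 4.7.3 counts every event but ends person-time at an unspecified event date, so numerator and denominator do not match

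*SAP*

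**What the plan says.** SAP 4.7.3 plans a table of the "rate of on-treatment symptomatic hypoglycemic events (Overall, and by time of day per ADA levels"). The rate is defined as "Number with hypoglycemic events/Total Person Years", and the next sentence adds: "If there are multiple events from an individual participant, all events will be counted".

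Total person-years is "cumulative total time to event date for participants with event + cumulative total of censoring time for participants without event". A participant with an event contributes the event date minus the first-dose date plus one day. A participant without one contributes the period from first dose to one day after the last dose. Both are in days, and no conversion to years is given.

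Four other places bear on this:

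- SAP 4.7 describes the measure as "number of events per participant year, will be analyzed descriptively in a table".
- SAP 4.7.3 treats hypoglycemia as treatment-emergent "up to 1 day after the last IMP injection".
- SAP 4.7.1 defines cumulative exposure as the "sum of days of the duration of treatment exposure for all participants divided by 365.25", and SAP 4.7.4.2 uses cumulative exposure as the denominator for the product-complaint rate.
- Protocol 8.7.8.2 counts repeat episodes and says that the rate per person-years "will be reported overall and by level".

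**The concern.** Two coherent rates are possible. A recurrent-event rate divides all events by all time at risk. A first-event incidence counts each participant once and divides by time to the first event. The SAP pairs the numerator of the first with a denominator built like the second. Once a participant has reached the chosen event, any later events enter the numerator with no time at risk behind them.

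The rule is also open to interpretation. For a participant with several events the event date could be the first, the last or, if times are accumulated over events, each one in turn. Two programmers could report different rates from the same data.

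Because the denominator depends on who has an event, it also changes with the event category. Day and night rates would then not sum to the overall rate.

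Hypoglycemia is a listed safety endpoint and an important identified risk of the product (Protocol 1.3). With a single arm, the absolute rate is what readers will take away.

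**Working it through.** The documents state no hypoglycemia rate, event count or person-year total, so there is no planned figure to reproduce. The check compares the rate under the SAP rule with all events over all on-treatment time.

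**Inputs.** First dose is on Day 0 and Visit 7 on Day 112 (Protocol 13.1). The SAP's censoring formula gives (112 + 1) − 0 + 1 = 114 days, so τ = 114/365.25 = 0.3121 years. All participants are assumed to complete treatment. The event rates λ are assumptions, shown as a range. Between-participant variation runs from none (Poisson) to strong clustering (gamma frailty, shape k = 0.25).

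**Formulas.** Inflation is τ divided by the mean person-time credited per participant.

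- First event, Poisson: credited time = (1 − exp(−λτ))/λ.
- First event, gamma: credited time = the integral from 0 to τ of (1 + λt/k)^(−k) dt.
- Last event, Poisson: credited time = τ + τ·exp(−λτ) − (1 − exp(−λτ))/λ.
- Every event's time summed: a participant with n ≥ 1 events is credited nτ/2 on average.

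The last-event and every-event results for both distributions come from simulating 3,000,000 participants per setting. As an example at λ = 2 (Poisson, first event), λτ = 0.6242 and inflation = 0.6242/(1 − exp(−0.6242)) = 1.344.

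**Change in the reported rate (k = 0.25 and Poisson as limits):**

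| Assumed rate per year | First event | Last event | Every event summed |
|---|---|---|---|
| 0.25 | +4% | +3 to 4% | +3 to 4% |
| 0.5 | +7 to 8% | +5 to 8% | +4 to 7% |
| 1 | +12 to 16% | +8 to 15% | +3 to 13% |
| 2 | +20 to 34% | +11 to 26% | −4 to +18% |

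At 5 per year the every-event reading ranges from −28% to +1%, because the same days are counted more than once.

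**Worked example (assumed data).** There are 100 participants with 114 days each. Thirty have 3 events, at 40, 60 and 80 days from first dose, which makes 90 events.

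- All exposure: 90/(100 × 114/365.25) = 2.88 per year.
- First event: 90/((70 × 114 + 30 × 40)/365.25) = 3.58 (+24%).
- Last event: 90/((70 × 114 + 30 × 80)/365.25) = 3.17 (+10%).
- Every event: 90/((70 × 114 + 30 × 180)/365.25) = 2.46 (−15%).

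**Additivity (first-event reading, Poisson).** Take true rates of 1.5 by day and 0.5 by night, 2.0 overall. Multiplying each by its inflation gives 1.88 by day and 0.54 by night, which sum to 2.42. The reported overall rate would be 2.69.

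**The case against.** The strongest case is that little depends on this rate. It is descriptive, the study has one arm, and no test, sample size or decision uses it. Event counts and cumulative participant-years are reported separately, so a reader could largely rebuild the overall rate. At low event rates, as in a single ADA level at night, the distortion is a few percent. All of this stands, and it limits the importance of the point. It does not make the table correct.

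The ambiguity may also be narrower than described. The table uses survival terms, and the section's only time-to-event figure concerns a first event, so first event is the natural reading. The every-event reading is the least likely, because the table cell sums over participants, and the downward results come only from it. That is fair, but of the three readings the first-event one gives the largest upward bias.

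The rate formula's wording could mean participants with an event, which would give a valid first-event incidence. The sentence that follows it rules this out, as do SAP 4.7 and Protocol 8.7.8.2.

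The SAP does not say in so many words that person-years are recalculated for each row. This follows from splitting participants by whether they had the event, but it is an inference.

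Lastly, full exposure is the ordinary meaning of an event rate per person-years. The protocol does not define the term.

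**Conclusion.** The point holds. The rule as written does not yield the events-per-participant-year measure that SAP 4.7 and Protocol 8.7.8.2 describe, and it leaves the event date undefined. If time stops at the first or last event, the bias is upward: 3 to 8% at assumed rates up to 0.5 per year, and 11 to 34% at 2 per year. If every event's time is summed, the direction can reverse. These sizes rest on assumed event rates, assumed clustering and full 114-day follow-up. The mismatch itself rests only on the SAP text. It should be corrected before the tables are programmed, but it does not affect the primary or key secondary analyses.

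**What to change.** In SAP 4.7.3:

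1. Define total person-years as the sum, over all safety-set participants with or without an event, of ((last dose date + 1) − first dose date + 1)/365.25. This is the SAP's own censoring formula and matches its hypoglycemia window. It is one day per participant longer than the exposure in SAP 4.7.1, a difference of under 1% for 114 against 113 days. Use the same denominator in every row.
2. Define the numerator as the number of hypoglycemic events. Keep the planned categories and breakdowns.

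Time-to-event person-time should be kept for the time-to-first-event figure. It could also serve a separately labelled first-event incidence that counts each participant once.

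As a separate matter, reconcile the SAP's restriction of the rate to symptomatic events with the protocol, which asks for it overall and by level.

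The cost is one table cell, removal or relabelling of the two time columns, one word in the formula, and a simpler program. No new data are needed.
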